9.3.2.2. Secondary outcomes

9.3.2.2.1. Time trends in patient characteristics and anticoagulation treatment patterns

Description by calendar year of:

- Age group at index date
- Medical history at index date
- Class of anticoagulation therapy at initiation

9.3.2.2.2. Effectiveness outcome

A secondary outcome on effectiveness will be recurrent symptomatic VTE.

Potential cases will be identified using diagnostic codes according to the different coding systems in the data sources (preliminary list in [Annex 3](#)). Care for children with an incident VTE takes place in inpatient setting (i.e., hospital stay requiring at least one night). At the same time, it is highly likely that VTE diagnoses are recorded as complications, secondary to other main reasons for a hospital stay. Therefore, the main definition for VTE diagnoses will be based on a sensitive approach including all primary/main and secondary diagnoses captured during hospitalization. Thus, a case of recurrent symptomatic VTE will be defined as a hospitalization with one of the following primary, related or associated diagnoses:

- DVT
- PE
- Cerebral vein or sinus thrombosis
- Central venous catheter related thrombosis
- Any VTE resulting in death.

A sensitivity analysis is planned for VTE outcome with a more restrictive definition using only main/primary diagnostic codes, excluding secondary diagnostic codes.

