9.2.2. Study time frame

9.2.2.1. Index date and follow-up

The index date will be the day of initiation of any anticoagulation therapy (rivaroxaban oral suspension or SOC). Patients will be assigned to two exposure categories, rivaroxaban or SOC, according to their actual use of the respective anticoagulation therapy. They may contribute time at risk to more than one exposure category if they switch from one to the other. More specifically, patients will be allowed to switch multiple times between SOC and rivaroxaban and contribute time accordingly to both exposure categories, as long as the same anticoagulant treatment period is continuing.

Patients will be followed from the index date to the earliest of the following censoring criteria:

- End of the anticoagulation treatment period, i.e., discontinuation of all study drugs (rivaroxaban and SOC),
- Death,
- Disenrollment/de-registering/emigration or last available data,

- End of the study period.

Moreover, patients will be followed until the first occurrence of each safety/effectiveness outcome event, with time at risk defined separately for each outcome analysis.

If patients have another initiation of anticoagulant therapy (SOC or rivaroxaban) for a VTE diagnosis before the age of two years, i.e., another qualifying anticoagulant treatment period for a recurrent VTE observed during the inclusion period for which they fulfil all inclusion and exclusion criteria (including a 6-month washout period), they will be allowed to enter the study cohort again, with a new index date.

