9.2.3. Selection criteria

9.2.3.1. Inclusion criteria

Participants are eligible to be included in the study only if all of the following criteria apply:

- Evidence of initiation of an anticoagulant therapy (index drug), either rivaroxaban oral suspension or other anticoagulation therapies (heparins, VKAs, other DOACs). Initiation will be defined as a first record of any anticoagulation therapy (rivaroxaban or SOC) without any anticoagulation therapy in the previous 6 months, or since date of birth for children less than 6 months (see codes for anticoagulant drugs in [Annex 3](#)).
- Evidence of a prior VTE diagnosis (index VTE), defined as the presence of at least one primary/main or secondary diagnosis code for VTE recorded in inpatient setting in the previous 30 days (see preliminary list for VTE codes in [Annex 3](#)).
- Age less than two years on index date.
- Baseline period for availability of patient data history in the data source. A minimal baseline period of six months before index date for children aged between six months and two years, and a baseline period since birth for children less than six months of age will be required.

According to its indication, rivaroxaban oral suspension should be used after at least five days of initial parenteral anticoagulation treatment. In order to describe the actual clinical practice in real world settings, there will no requirement on this initial parenteral anticoagulation treatment to include patients in the study population, so patients will be identified independently of this. In theory, all patients receiving rivaroxaban should be switchers. In practice, they may appear as initiating directly with rivaroxaban: the observed initial anticoagulant therapy might be different from the actually received initial therapy, if patients have switched drug during hospital stay and if inpatient drug data is not captured. Depending on availability of inpatient drug data in each data source, the observed initiation of the anticoagulant therapy will be identified either in outpatient or in inpatient setting, as shown in [Figure 2](#) below (see [Section 9.4](#)).

SOC for treatment of VTE in children usually include UFH, LMWH and VKA and may vary across countries. With other DOACs receiving indication for VTE in paediatrics, SOC may also evolve over time.

Figure 2 Visualization of patient journey

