9.9. Limitations of the research methods

The use of secondary data that has not been primarily collected for research purposes comes with specific limitations.

Selection bias

- All patients fulfilling eligibility criteria will be included in the study. The data sources in the different countries differ in terms of contents and expected coverage. Most have a national coverage, while SIDIAP which only covers ~75% of Catalonia is also considered representative of the Spanish population. Therefore, the selection bias is considered to be low with respect to the target countries.

Information bias

- Exposure data
 - Anticoagulation therapy is expected to be initiated during hospital stay and renewed for outpatient use. According to its indication, rivaroxaban oral suspension should be used after at least five days of initial parenteral anticoagulation treatment. Thus, in theory, all patients receiving rivaroxaban should be switchers from parenteral anticoagulant treatment. In practice, the capacity to observe the actual initial parenteral anticoagulation treatment and its duration will depend on the availability of inpatient drug data in the selected data sources. This will be feasible when

inpatient drug data is captured, e.g., in the Danish SMR (soon available, with data collected since May 2018) and in SIDIAP through linkage with hospital dispensation medication. However, inpatient drug data is not captured in SNDS and in Swedish national registers, which represents a risk of exposure underestimation. In this latter situation, the information on anticoagulation therapy and its duration will be based on outpatient prescriptions only, at a time when patients may have already, or not yet, stopped the initial parenteral anticoagulation treatment, and switched to maintenance therapy like rivaroxaban. Hence, when patients will have switched to rivaroxaban during hospital stay in an unobservable period in the data source, they will appear as initiating anticoagulation therapy with rivaroxaban, and not switchers. To avoid immeasurable time bias, the index date will be the first observed record of anticoagulation therapy in each data source, whether it occurs during inpatient stay or afterwards.

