is also possible that a bleeding occurs while the child is already hospitalized for another reason being reported as the primary diagnosis. To mitigate this risk of misclassification, two definitions will be considered for the bleeding outcomes: in the main analysis, a sensitive approach considering all appropriate bleedings reported as primary, related, or associated diagnoses will be used as the primary definition to capture all bleedings that might represent a major bleeding or a CRNM bleeding. By increasing specificity, a sensitivity analysis restricted to those bleeding events reported as *primary* diagnoses during hospitalization will inform on the robustness of study findings.

- Recurrent symptomatic VTE. Children are likely to come to a specialist/hospital for a control visit or something related to their first VTE. On this occasion they might be recorded with a diagnosis of VTE even if this does not represent a recurrent VTE event. In order to minimize this risk of misclassification, the outcome of recurrent VTE will be restricted to VTE diagnoses recorded in inpatient setting, thus excluding control visits for VTE which most likely occur in secondary outpatient care. However, a risk of misclassification remains for children hospitalized for a long period or for other reasons than the index VTE, where it might be difficult to distinguish a recurrent VTE event from the index VTE. For this reason, the use of a primary definition of VTE diagnoses, including all primary/main and secondary diagnoses codes, and a secondary more specific definition restricted to primary VTE diagnoses reported through hospitalization will allow to test the robustness of the findings.

Other limitations

- **Impact of the small sample size**

The number of available children aged under two years with VTE is expected to be very low in most data sources due to VTE being a rare event in this population. For this reason, all analyses will be descriptive and no confirmatory comparison between exposure categories will be performed.

To comply with GDPR, cell suppression is required to mitigate the risk of re-identification in most countries. Consequently, this is a major limitation for analyses in most data sources, except SNDS in France. Besides, due to the small sample size and low frequency of the safety and efficacy outcomes, it is expected that these analyses should only be feasible in the SNDS.

- **Missing data**

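### The main definition of recurrent VTE has no rule separating it from the index VTE episode, so index-episode stays and carried-forward codes can be counted as recurrences

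*Protocol*

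**What the plan says.** - **Outcome.** Section 9.3.2.2.2 adopts "a sensitive approach including all primary/main and secondary diagnoses captured during hospitalization" and concludes that "a case of recurrent symptomatic VTE will be defined as a hospitalization with one of the following primary, related or associated diagnoses". It sets no condition on a new admission, a gap or a new site.
- **Index VTE.** Section 9.2.3.1 qualifies a child by "at least one primary/main or secondary diagnosis code for VTE recorded in inpatient setting in the previous 30 days".
- **Start of follow-up.** Section 9.2.2.1 starts follow-up at anticoagulant initiation. Section 9.9 says that "Anticoagulation therapy is expected to be initiated during hospital stay and renewed for outpatient use", and that "the index date will be the first observed record of anticoagulation therapy in each data source, whether it occurs during inpatient stay or afterwards".
- **Sources.** Section 9.9 says that "inpatient drug data is not captured in SNDS and in Swedish national registers". Inpatient drug records are expected only in Denmark and, by linkage, in SIDIAP.
- **Counting.** Section 9.7.4 takes the first occurrence of each outcome within time at risk.
- **Recognised risk.** For long stays, or stays for another reason, section 9.9 concedes that "it might be difficult to distinguish a recurrent VTE event from the index VTE". Its two answers are to use inpatient diagnoses only, and to run a sensitivity analysis on primary diagnoses (section 9.7.6.3).

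**The concern.** The event that brings a child into the cohort and the event counted as the outcome rest on the same evidence, an inpatient VTE code in any position. The stated definition gives no means of telling them apart.

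This opens three routes to a false recurrence:

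1. Where an inpatient drug record sets the index date, follow-up can begin inside the VTE-coded index stay.
2. A transfer or contiguous stay after the index date repeats the VTE code of the same episode. This can happen in any source.
3. A later admission for another reason lists the known VTE as an associated diagnosis. This too can happen in any source. It is plausible because section 7.2 says that more than 80% of affected children have underlying risk factors, and section 9.3.2.2.2 itself expects VTE to be coded often as secondary to another reason for the stay.

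The expected proportion with a true recurrence is only 1.2% to 3.0%, so a small share of false positives can distort the incidence. Because only the first occurrence counts, a false event also ends the child's time at risk for this outcome and can hide a later true recurrence.

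**Working it through.** **1. The plan's own expected counts (section 9.5.2, Table 6).** Inputs are 846 children overall and 650 in SNDS, of whom 219 are on rivaroxaban, with recurrence of 1.2% (rivaroxaban) and 3.0% (comparator). The all-patient rows reproduce with the simple mean of the two, 2.1%:

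- Overall: 846 × 0.021 = 17.8, stated as 18.
- SNDS: 650 × 0.021 = 13.65, stated as 14.
- SNDS on rivaroxaban: 219 × 0.012 = 2.63, stated as 3.

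Weighting SNDS by expected exposure gives 219 × 0.012 + 431 × 0.030 = 2.63 + 12.93 = 15.6. Hence 14 to 16 recurrences in SNDS.

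**2. Effect of false positives in SNDS.** Let f be the share of children without a recurrence who nevertheless have a qualifying VTE-coded stay. The documents give no value for f, so a range is shown. False events = f × (650 − 13.65).

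| f (assumed) | False events | Total counted | Share that is true |
|---|---|---|---|
| 1% | 6.4 | 20.0 | 68% |
| 2% | 12.7 | 26.4 | 52% |
| 5% | 31.8 | 45.5 | 30% |

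False events equal true ones at f = 13.65 / 636.35 = 2.1%. With the weighted count it is 15.56 / 634.44 = 2.5%.

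**3. SNDS rivaroxaban group.** Section 9.7.8 suppresses French counts below ten. Solving 2.63 + f × (219 − 2.63) = 10 gives f = 7.37 / 216.37 = 3.4%. At that point about 74% of the ten reportable events would be false.

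**4. Denmark and SIDIAP.** Expected children: 52 + 45 = 97, or 97 / 846 = 11.5% of the total. Expected recurrences: 97 × 0.021 = 2.0. If the index stay were counted for a share s of the other 95.0 children, the false events would be 23.7 at s = 25%, 47.5 at s = 50% and 95.0 at s = 100%. The value of s depends on how a stay is dated, which the protocol does not fix. If stays are dated by admission, an index stay that began before the index date falls outside time at risk.

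**5. What each remedy removes.**

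| Source of false event | Inpatient codes only (plan) | Primary diagnosis only (plan) | New-admission rule (proposed) |
|---|---|---|---|
| Outpatient control visit | Removed | Removed | Not relevant |
| Index stay, transfer or contiguous stay, VTE coded secondary | Kept | Removed | Removed |
| Index stay, transfer or contiguous stay, VTE coded primary | Kept | Kept | Removed |
| Later admission, known VTE coded secondary | Kept | Removed | Kept |
| Later admission for the index VTE, coded primary | Kept | Kept | Kept |

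The third row is the gap that neither planned measure closes. The fourth row is what the new-admission rule does not touch, so both tools are needed together.

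**The case against.** The strongest case against has five parts.

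- **The index stay may never enter time at risk.** Inclusion needs a VTE code before the index date, and outcomes count only after it. One record would have to be dated differently for the two purposes. This stands in part: a reader might infer that the index event is always counted, and the documents do not support that. They do not exclude it either, because a hospitalisation is an interval and no dating rule is given. Transfers and contiguous stays do not depend on this point.
- **The index-stay route is confined to small sources.** This stands. Only Denmark and SIDIAP are expected to have inpatient drug records, and Table 4 marks recurrent VTE there as below the disclosure threshold. In SNDS and Sweden the index date is normally a first outpatient prescription, after the index stay.
- **A new-admission rule would not reduce the SNDS excess from carried-forward codes.** This stands. A later admission listing the old VTE satisfies the rule. A reader might infer that the rule removes the excess calculated above, and it does not.
- **The sensitive definition is deliberate, and a primary-diagnosis analysis is planned.** The reason given, that VTE is often coded as secondary, is fair. But it supports a wide choice of code position, not the absence of an episode boundary.
- **Outcome definitions are left to the SAP.** Section 9.7.1 does defer variable definitions. However, section 9.3.2.2.2 states the main case definition and section 9.9 states the chosen mitigation. The comment is on what those two sections fix.

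**Conclusion.** The point holds as a recommended change to a secondary, descriptive outcome. The protocol recognises that index and recurrent VTE may be confused, yet its main definition has no boundary between them. Its sensitivity analysis leaves in place any index-episode stay with VTE coded as primary.

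Its size is conditional. Against 14 to 16 expected recurrences in SNDS, false positives in 2.1% to 2.5% of the remaining children would equal the true count. The index-stay route concerns about 97 of 846 children and depends on how stays are dated.

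A reader might infer that false recurrences will outnumber true ones, or that a wrong rivaroxaban incidence will become reportable in France. The documents do not support either as a forecast, because they give no rate of carried-forward coding. What they support is that an outcome this rare tolerates very little misclassification.

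**What to change.** In section 9.3.2.2.2, count a recurrence only for a VTE-coded stay whose admission date is after discharge from the index VTE episode, with transfers and contiguous stays chained into one episode. Apply the same rule to the primary-diagnosis sensitivity analysis in section 9.7.6.3.

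Present that primary-diagnosis result next to the main result. The difference between them is the number of children counted on secondary codes alone, which bounds the error from carried-forward secondary codes on later admissions. Do not claim that the new-admission rule itself removes that error.

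Add to section 9.9 that true recurrences during the index episode are not counted.

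The cost is one sentence in the definition, one in the limitations, and a stay-chaining step in the programming, all before data extraction. The loss is the true recurrences that occur before discharge from the index episode.

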9.3.2.2.3. Specialty and care setting of physicians

- Physician specialty and care settings (inpatient care, secondary outpatient care, primary care) for prescriptions of anticoagulation therapy

9.4. Data sources

9.4.1. Feasibility assessment

The study will make secondary use of existing data from multiple countries. A feasibility assessment was conducted with the aim to evaluate large electronic healthcare databases to guide the selection of the most relevant data sources for addressing the research question and study objectives. A report on this feasibility assessment is provided as a stand-alone document (see [Annex 1](#)) which is available upon request.

The choice of final data sources was guided by the following criteria:

- Representativeness of the overall population covered by the data source and the target population of children under two years with VTE receiving anticoagulant therapy
- Countries in which the estimated cumulative average number of children under two years with VTE and exposed to rivaroxaban in the data source is at least 15 during the inclusion period 2021-2026 (see [Section 9.5.2](#))
- Availability of the information required to meet the study objectives, including the ability to identify and describe the target population of children under two years with VTE, and the availability and quality of exposure and outcomes data
- Procedure and timelines for data access
- Coverage of different regions in Europe

Based on the overall rating, the final list of recommended data sources include:

- Système National Des Données De Santé (SNDS) in France
- National health registers in Sweden
- National health registers in Denmark
- Sistema d'Informació per al Desenvolupament de l'Investigació en Atenció Primària (SIDIAP) in Spain

Depending on the actual accrual of patients over the study period, additional data sources might need to be considered in future.

General characteristics of the data sources are provided in [Table 3](#).

Table 3: Summary characteristics of data sources

Country	Data source name	Data source type	Population size (active)	Source population coverage (%)	Data lag time	Coding system for drugs	Drugs data	Coding system for diagnoses	Diagnoses and procedures data
Denmark	MBR, NPR, RMPS, SMR, Register of causes of death	National health registers	5.8 million	100%	2-13 months	ATC	Drugs dispensed at community pharmacies. Drugs given in hospitals (expected release in 2022)	ICD-10	Secondary outpatient care, inpatient care, emergency
Sweden	MBR, NPR, PDR, Cause of death register	National health registers	10.3 million	100%	14 days-12 months	ATC	Prescribed drugs for outpatient use, dispensed drugs through retail pharmacies, use of OTC drugs, reimbursed drugs	ICD-10	Inpatient care and specialized outpatient care
France	SNDS	Claims database	66 million	99%	3-7 months	ATC, UCD, CIP	Dispensed drugs through retail pharmacies, reimbursed drugs, some costly drugs administered in hospital	ICD-10	Inpatient care, some ambulatory long-term diseases, all procedures
Spain (Catalonia)	SIDIAP	EMR database	5.6 million	74% (from Catalonia)	12 months	ATC	Primary care prescriptions, drugs dispensed through retail pharmacies. Possible linkage with hospital pharmacy drugs databases	ICD-9, ICD-10-CM	Primary care linked to hospital admissions and deaths

ATC = Anatomical Therapeutic Chemical (Classification System); CIP = Club Inter-Pharmaceutique; CM = Clinical Modification; EMR = Electronic Medical Records; ICD = International Classification of Diseases; MBR = Medical Birth Register; NPR = National Patient Register; PDR = Prescribed Drug Register; RMPS = Register of Medicinal Products Statistics; SIDIAP = Sistema d'Informació per al Desenvolupament de l'Investigació en Atenció Primària; SNDS = Système National Des Données De Santé; SMR = Hospital Patient Medication Register; UCD = Unité Commune de Dispensation.

The feasibility of study objectives is summarized in [Table 4](#).

Table 4: Feasibility of study objectives in the data sources

Data sources	Danish national registers	SNDS	SIDIAP	Swedish national registers
Primary objectives				
To describe clinical characteristics and demographics of patients using anticoagulation therapy for the treatment of VTE (rivaroxaban oral suspension or SOC)	Yes	Yes	Yes	Yes
To describe use of anticoagulation therapy (including selected drug, dose, and duration) for treatment of VTE	Yes ^a	Yes	Yes ^a	Yes
To describe the incidence and severity of bleeding (major bleeding, and CRNM bleeding) according to anticoagulation therapy (rivaroxaban oral suspension or SOC)	BT ^b	Yes	BT ^b	BT ^b
Secondary objectives				
To describe time trends in patient characteristics and anticoagulation treatment patterns at the population-level over the study period	Yes ^a	Yes	Yes ^a	Yes
To describe the incidence of recurrent symptomatic VTE according to anticoagulation therapy (rivaroxaban oral suspension or SOC)	BT ^b	BT ^b	BT ^b	BT ^b
To describe specialty and care setting of physicians who prescribe anticoagulation therapy (rivaroxaban oral suspension or SOC)	TBD	Yes ^c	TBD	Yes

BT = Below threshold; SIDIAP = Sistema d'Informació per al Desenvolupament de l'Investigació en Atenció Primària; SNDS = Système National Des Données De Santé; SOC = Standard of care; TBD = To be defined; VTE = Venous thromboembolism;

^a Include intrahospital treatment

^b Estimated average number of outcomes below disclosure threshold (see [Section 9.5.2](#) for details)

^c Partially available

In the next section details for the data sources are displayed.

